24 PREMATURE DISCONTINUATION OF THE STUDY OR PREMATURE CLOSE-OUT OF A SITE

24.1 Decided by the Sponsor in the following cases:

- 1. In the event the results of the Clinical Trial do not appear to be scientifically convincing to the Sponsor;
- 2. If the aim of the Clinical Trial has become outdated or is no longer of interest;
- 3. If the information on the product leads to doubt as to the benefit/risk ratio;
- 4. If the Investigator has received from the Sponsor all Investigational Product, means and information necessary to perform the Clinical Trial and has not included any patient after a reasonable period of time mutually agreed upon;
- 5. In the event of breach by the Investigator of a fundamental obligation under this agreement, including but not limited to breach of the Clinical Trial Protocol, breach of the applicable laws and regulations or breach of the ICH guidelines for GCP;
- 6. If the total number of patients are included earlier than expected; In any case the Sponsor will notify the Investigator of its decision by written notice.

24.2 Decided by the Investigator

The Investigator must notify (30 days' prior notice) the Sponsor of his/her decision and give the reason in writing. In all cases (decided by the sponsor or by the Investigator), the appropriate Ethics Committee(s) (IRB/EC) and Health Authorities should be informed.

25 CLINICAL TRIAL PROTOCOL AMENDMENTS

All appendices attached hereto and referred to herein are made part of this Clinical Trial Protocol. The Investigator should not implement any deviation from, or changes of the Clinical Trial Protocol without agreement by the sponsor and prior review and documented approval/favorable opinion from the IRB/EC of an amendment, except where necessary to eliminate an immediate hazard(s) to clinical trial patients, or when the change(s) involves only logistical or administrative aspects of the trial. Any change agreed upon will be recorded in writing, the written amendment will be signed by the Investigator and by the Sponsor and the signed amendment will be filed with this Clinical Trial Protocol. Any amendment to the Clinical Trial Protocol requires written approval/favorable opinion by the IRB/EC prior to its implementation, unless there are overriding safety reasons. In some instances, an amendment may require a change to the Informed Consent Form. The Investigator must receive an IRB/EC approval/favorable opinion concerning the revised Informed Consent Form prior to implementation of the change.

APPENDIX A: SCHEDULE OF EVENTS

Visit Name	Screening	Washout phase	Baseline Day 0	Day 5	Day 14 (Week 2)	Day 28 (Week 4)	Day 56 (Week 8)	Early Termination Visit	Comments/Clarification
Visit Number	V1		V2		V3	V4	V5		
Visit Window in days	-21 to -14	-14 to -1	0	+/-2	+/-2	+/-2	+/-3		
Informed Consent	X								Informed consent will occur prior to any protocolmandated procedures, including the stopping of any excluded therapies.
Inclusion / Exclusion Criteria	X		X						
Demographics	X								
Medical History	X		X						
Concomitant Medications	X		X		X	X	X	X	
Physical Exam	X						X	X	
Vital Signs	X		X		X	X	X	X	Height and weight will be assessed at screening; BP, pulse, respiration rate, and

									temperature will be assessed at each visit. Smoking status will be recorded at Screening
eDiary	X	X	X	X	X	X	X	X	Subjects will be provided eDiary to be completed at home daily and in-clinic. At home eDiary will include WI-NRS, AI-NRS, rescue medication, dose administration, and local skin tolerability. In clinic eDiary will include POEM and 5-D Pruritus Scale. eDiary will be reviewed at the baseline visit to determine eligibility.
POEM	X		X		X	X	X	X	Patient reported assessment by ePRO
5-D Pruritus Scale	X		X		X	X	X	X	Patient reported assessment by ePRO
IGA	X		X		X	X	X	X	Clinician assessment by eCOA
EASI	X		X		X	X	X	X	Clinician assessment by eCOA
Itch Numeric Rating Scale (NRS)	X	X	X	X	X	X	X	X	Patient reported assessment by ePRO
Clinical Labs	X					X		X	Patients should fast for at least 8 hours before the test but optional at screening. Blood and urine for clinical

								(if visit occurs before Day 28)	chemistry will be shipped to the central lab for processing. Chemistry, Hematology, Lipid Panel, and Urinalysis will be done at Screening and Day 28. Serology will only be done at Screening. Kits and lab manuals will be provided by a central lab.
Urine pregnancy test for WOCBP	X		X			X	X	X	
IWRS			X						
Investigational Product compliance			Х		X	X		X	Weights of dispensed and collected bottles to be recorded following instructions provided to sites.
Dispense study drug			X		X				
Application of study drug			X	X	X	X			First application of study drug will occur in the office under the supervision of the study staff.
Phone call to subjects		X		X					Call to initiate washout phase will be placed once results of screening clinical

									labs are finalized. Call on Day 5 will be made to counsel subjects on the use of IP and eDiary recordings, as well as answer any questions.
Collect study drug					X	X		X	
Study counseling	X	X	X	X	X	X			Subjects will be counseled at each visit on the appropriate use of IP, eDiary entries and use.
AE monitoring	X		X		X	X	X	X	AE will be monitored from screening to follow-up. After informed consent, but prior to study drug administration, only SAEs caused by a protocolmandated intervention will be collected

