8.9 Study Drug Discontinuation

Subjects will be discontinued from study drug treatment in the following events:

- The subject experiences a Grade 2 or higher treatment emergent AE that is assessed as likely related to study drug
- The subject receives treatment with an excluded therapy or has a clinically significant change in dose or frequency of allowed adjunctive therapies during the treatment period
- The female subject becomes pregnant or female partner of a male subject becomes pregnant or is breastfeeding

Discontinuation from study drug treatment may also occur for any of the following reasons:

- Subject decision to discontinue study drug treatment, or subject decision to withdraw consent from the study
- Any medical condition that may jeopardize the subject's safety if study drug is continued, in the investigator's and/or Sponsor's opinion
- Discontinuation is deemed to be in the best interest of the subject, in the investigator's and/or Sponsor's opinion

Subjects who discontinue treatment with study drug prior to completing the treatment period will have an ETD visit within 7 days after their last dose of study drug in addition to a follow-up visit

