10.6.4 Day 5- Phone call to patient

The Day 5 visit is a telephone visit that occurs 5 days (±2 days) after the Baseline visit. Study staff will discuss IP application with the subject, answer any questions and counsel the subject on any other matters related to the study.

- phone call to subjects
- application of study drug
- study counseling

10.6.5 Day 14 and Day 28 study visits – Visit 3 and Visit 4

- concomitant medications
- vital signs
- blood for clinical chemistry and hematology (Day 28)
- urine pregnancy test (for women of childbearing potential) (Day 28)
- NRS assessment
- POEM questionnaire
- Pruritus 5-D questionnaire
- IGA scoring assessment
- EASI scoring assessment
- obtain study medication weight for Investigational Product compliance
- dispense investigational product to patient (Day 14)
- collect study medication
- application of study drug
- eDiary
- study counseling
- recording of AEs if any

10.6.6 Day 56-End of Study Visit – Visit 5

- concomitant medications
- vital signs
- physical exam
- urine pregnancy test (for women of childbearing potential)
- NRS assessment
- POEM questionnaire
- Pruritus 5-D questionnaire
- IGA scoring assessment
- EASI scoring assessment
- eDiary
- recording of AEs if any

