10.6.8 Early Termination Visit

Every attempt should be made to complete all visits during the defined window periods. Subjects who do not complete all required study visits and withdraw from the study before the Day 56 final visit will be asked to complete the Early Termination Visit.

During the visit, the following will be obtained:

- concomitant medications
- vital signs
- physical exam
- urine pregnancy test (for women of childbearing potential)
- NRS assessment
- POEM questionnaire
- Pruritus 5-D questionnaire
- IGA scoring assessment
- EASI scoring assessment
- blood for clinical chemistry and hematology (if visit occurs before Day 28)
- eDiary
- collect study medication (if visit occurs before Day 28)
- obtain study medication weight for Investigational Product compliance
- recording of AEs if any

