2.2 Schedule of Activities

| Visit Name# | Screening | Washout | Baseline | Day 5 | Day 14 | Day 28 | Day 56 | Early |
|------------------------------------|------------|-----------|----------|-------|----------|---------------------------------------|----------|------------|
| | L C | phase | Day 0 | 2 | (Week 2) | (Week 4) | (Week 8) | Terminatio |
| | | 1 | 2 | | , , | , , , , , , , , , , , , , , , , , , , | × , | n Visit |
| Visit Number | V1 | | V2 | | V3 | V4 | V5 | |
| Visit Window in days | -21 to -14 | -14 to -1 | 0 | +/-2 | +/-2 | +/-2 | +/-3 | |
| Informed Consent | Х | | | | | | | |
| Inclusion / Exclusion Criteria | X | | Х | | | | | |
| Demographics | Х | | | | | | | |
| Medical History | Х | | Х | | | | | |
| Concomitant Medications | Х | | Х | | X | Х | Х | X |
| Physical Exam | X | | | | | | X | X |
| Vital Signs | X | | Х | | X | Х | Х | X |
| eDiary | X | Х | Х | Х | X | Х | Х | X |
| POEM | X | | Х | | X | Х | Х | X |
| 5-D Pruritus Scale | X | | Х | | X | Х | Х | X |
| IGA | Х | | Х | | X | Х | Х | X |
| EASI | Х | | Х | | X | Х | Х | X |
| Itch Numeric Rating Scale (NRS) | X | Х | Х | Х | X | Х | Х | X |
| Clinical Labs | X | | | | | Х | | X* |
| Urine pregnancy test for WOCBP | X | | Х | | | Х | X | Х |
| IWRS | | | Х | | | | | |
| Investigational Product compliance | | | Х | | X | Х | | X |
| Dispense study drug | | | Х | | X | | | |
| Application of study drug | | | Х | Х | X | Х | | |
| Phone call to subjects | | Х | | Х | | | | |
| Collect study drug | | | | | X | Х | | X |
| Study counseling | Х | Х | Х | Х | Х | Х | | |

CLINICAL RESEARCH OPTIMIZED™

Protocol: PRB244-01 Confidential STATISTICAL ANALYSIS PLAN

Version 3.0 12-Jan-22

| Visit Name# | Screening | Washout | Baseline | Day 5 | Day 14 | Day 28 | Day 56 | Early |
|----------------------|------------|-----------|----------|-------|----------|----------|----------|------------|
| | | phase | Day 0 | | (Week 2) | (Week 4) | (Week 8) | Terminatio |
| | | | | | | | | n Visit |
| Visit Number | V1 | | V2 | | V3 | V4 | V5 | |
| Visit Window in days | -21 to -14 | -14 to -1 | 0 | +/-2 | +/-2 | +/-2 | +/-3 | |
| AE monitoring | X | | X | | X | X | X | X |

#: Comments/clarification to visits in table below.

*: if visit occurs before Day 28

.....

| Protocol: PRB244-01 | STATISTICAL ANALYSIS PLAN |
|---------------------|---------------------------|
| Confidential | |

Version 3.0 12-Jan-22

| Visit Name | Comments/Clarification |
|---------------------------------|--|

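### Early-termination laboratory tests depend on the calendar day and not on whether the Week 4 sample was taken, so some late leavers have no scheduled post-dose laboratory test

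*Protocol*

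**What the plan says.** Appendix A of the protocol marks clinical laboratory tests at Screening, Day 28 and Early Termination, and qualifies the last with "if visit occurs before Day 28". Its comment column confirms the fixed time points: "Urinalysis will be done at Screening and Day 28". The visit list in Section 10.6.8 carries the same condition, as does the footnote to SAP Section 2.2.

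The list for the Day 14 and Day 28 visits (Section 10.6.5) restricts blood to the second of them: "blood for clinical chemistry and hematology (Day 28". The Day 56 list (Section 10.6.6) contains no blood or urine chemistry.

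Two provisions govern when an Early Termination visit can happen. Under Section 8.9, subjects who stop study drug early "will have an ETD visit within 7 days after their last dose of study drug in addition to a follow-up visit". Under Section 10.6.8, subjects who "withdraw from the study before the Day 56 final visit will be asked to complete the Early Termination Visit". The Week 4 visit has a window of 2 days either side of Day 28 (Appendix A and SAP Section 2.2).

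For study drug, Section 10.6.8 says "collect study medication (if visit occurs before Day 28", while Appendix A and SAP Section 2.2 mark collection at Early Termination without any condition.

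**The concern.** The date stands in for what matters, namely whether a post-dose sample already exists. It fails for a subject who has no Week 4 visit and is first seen for Early Termination on Day 28 or later: the Week 4 sample was not taken, the Early Termination rule does not ask for one, and no later visit does.

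Change in laboratory parameters after exposure is a named safety endpoint (protocol Section 4.2, SAP Section 3.2.4). The SAP laboratory summaries (Tables 14.3.4.1.1 to 14.3.4.3.2) draw post-dose values only from Week 4 and Early Termination, and SAP Section 7.6 plans no imputation for them. The subjects affected have received most of the 28-day course. They may include some whom Section 8.9 takes off drug for an adverse event judged likely related. Those are subjects for whom a safety summary should have data.

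**Working it through.** The plan states no figure to reproduce here, so the check is to trace the schedule and then count which stopping days reach the gap.

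**Where a post-dose sample is scheduled**

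| Visit | Laboratory tests scheduled? |
|---|---|
| Day 5 (telephone) | No |
| Day 14 | No |
| Day 28 (window Days 26 to 30) | Yes |
| Day 56 | No |
| Early Termination before Day 28 | Yes |
| Early Termination on or after Day 28 | No |

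**Inputs**

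- Possible last-dose days: protocol Days 0 to 27, the 28-day course, with Day 0 as the first dose.
- Delay from last dose to the Early Termination visit: 0 to 7 days (Section 8.9 and the synopsis).
- Week 4 window: ends on Day 28 + 2 = Day 30.
- Planned dropout: 576 − 480 = 96 subjects, and 96/576 = 16.7% (protocol Section 12.1).
- Assumptions, not in the documents: last dose uniform over the 28 days, delay uniform over the 8 values 0 to 7, and every dropout attends Early Termination.

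**Count**

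- All combinations: 28 × 8 = 224.
- Visit on or after Day 28: for last dose on day d there are d − 20 such delays, for d = 21 to 27. The sum is 1 + 2 + 3 + 4 + 5 + 6 + 7 = 28, and 28/224 = 12.5%.
- Visit after Day 30: for last dose on day d there are d − 23 such delays, for d = 24 to 27. The sum is 1 + 2 + 3 + 4 = 10, and 10/224 = 4.5%.
- Visit on Days 28 to 30: 28 − 10 = 18, and 18/224 = 8.0%.

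**Applied to planned dropout**

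| | All 96 leave during treatment | Half (48) leave during treatment |
|---|---|---|
| On or after Day 28 (12.5%) | 12.0 | 6.0 |
| After Day 30 (4.5%) | 4.3 | 2.1 |

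The lower row is the firmer one. A visit on Days 28 to 30 lies inside the Week 4 window and can be conducted as the Week 4 visit, with its laboratory tests. Those samples are lost only if the site records the visit as Early Termination, because SAP Section 6.5.10 tabulates visits as recorded on the CRF.

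The count leaves out subjects who stay on study, miss Week 4 and withdraw during follow-up. They meet the same rule. A missed Week 4 visit is foreseeable: SAP Listing 16.2.15.2 names Week 4 among the visits affected by COVID-19.

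**The case against.** A reader might infer that these subjects never have a post-dose laboratory test. The documents do not support that. Section 10.6.7 leaves assessments at unscheduled visits to the investigator, Section 11.7 asks in general terms for a full evaluation of non-completers where possible, and Section 13.7 requires follow-up of adverse events, including laboratory findings, until they normalise or stabilise. None of these requires a routine panel at Early Termination, so what stands is that none is scheduled. Listing shells 16.2.8.1 to 16.2.8.3 name Week 8 as a visit, but neither schedule provides a sample then, and a shell cannot create one.

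A reader might also take 12.5%, or 12 subjects, as the size of the gap. That ignores the Week 4 window. It also assumes that every dropout attends, although Section 7.4 names loss to follow-up and withdrawal of consent as the routes to early termination. The 16.7% covers dropout up to Day 56 (Section 11.6), so it includes subjects already sampled at Week 4. The treatment-period number could be zero. Follow-up withdrawals who missed Week 4 pull the other way.

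Finally, a reader might infer from the drug-collection line in Section 10.6.8 that late leavers' bottles are not collected, and are then counted as used up under SAP Section 7.5.1. That does not follow. The same list requires the medication to be weighed at Early Termination without condition, and Section 8.12 has partly used and unused product returned to the site. With the unconditional marks in both schedules, this shows a wording conflict and no more. It is separate from the laboratory rule and adds no weight to it.

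It is also fair to say that laboratory data are summarised descriptively, so no hypothesis test, efficacy estimate or error rate is affected.

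**Conclusion.** The gap is real and follows from the plan's own timing rules: last dose on any of Days 21 to 27 permits an Early Termination visit on Days 28 to 34, where no laboratory test is scheduled and none follows. Under the stated uniform assumptions and full attendance, the firm part is about 2 to 4 subjects. Visits on Days 28 to 30 that are recorded as Early Termination, and follow-up withdrawals without a Week 4 visit, come on top. The documents do not give the true number. This is a small gap in safety data, worth closing because closing it is cheap.

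**What to change.** For laboratory tests, in Appendix A, Section 10.6.8 and the footnote to SAP Section 2.2, replace the Day 28 condition by *if Week 4 laboratory samples were not taken*. Every subject who attends Early Termination without a Week 4 sample is then scheduled for one. It also spares a repeat draw in a subject whose Week 4 visit fell on Day 26 or 27 and who terminates before Day 28. The SAP edit only keeps the two schedules aligned.

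The cost is one routine blood and urine sample at a visit already attended, for a few subjects, plus a protocol amendment with IRB approval.

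Separately, reconcile the conditional drug-collection line in Section 10.6.8 with the unconditional marks in Appendix A and SAP Section 2.2. The same amendment can carry this.

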APPENDIX A continued:

Schedule of eDiary and Efficacy Assessments

eDiary (ePRO) is provided to subjects at the screening visit for daily entry at home (e.g., application on smartphone). Questionnaires and clinician assessments are recorded via ePRO/eCOA (e.g., tablet) or CRF during the site visits per schedule of events. Additional patient reported information include rescue medication use, dose administration confirmation, and adjunctive therapy use.

Device	Assessment	Frequency and Duration of Assessment
eDiary	WI-NRS	Once daily from Screening visit through the Follow-up visit
eDiary	AI-NRS	Once daily from Screening visit through the Follow-up visit
eDiary	Local Tolerability	Once daily from Day 1 to Day 7 of treatment
eDiary	POEM	Patient reported at site visits
eDiary	5-D Pruritus Scale	Patient reported at site visits
eCOA/CRF	IGA	Clinician assessment at site visits
eCOA/CRF	EASI	Clinician assessment at site visits

APPENDIX B: EXCLUDED MEDICATIONS/THERAPY

Excluded medication/therapy is listed below. The use of an excluded medication/therapy is a protocol violation and must be recorded in the CRF.

Within 4 weeks prior to Baseline through the Follow-up period

- Systemic immunosuppressive/immunomodulating drugs (i.e., methotrexate, cyclosporine, etc.).
- Immunoglobulin or blood products.
- Systemic corticosteroids (oral, IV, injectable)
- NK1-R antagonists
- Class III or higher topical corticosteroids or any topical anti-pruritic therapies (other than stable doses of low- or mid-potency topical corticosteroids or bland emollients)
- Systemic therapies with recognized anti-pruritic (e.g. tricyclic antidepressants, sedatives, tranquilizers, gabapentin, marijuana or other cannabinoids, opioid receptor agonists/antagonists) or pruritic (e.g. opioids, angiotensin-converting enzyme inhibitors, cocaine, antimalarials) properties
 - Stable doses of oral H1 antihistamines will be permitted
- Systemic immunosuppressive/immunomodulatory therapies (including but not limited to PDE4 inhibitors, cyclosporine, mycophenolate-mofetil, methotrexate, azathioprine, interferon-gamma, or phototherapy)
- Allergen immunotherapy
- Any investigational therapy
- Strong CYP3A4 inhibitors, such as
 - boceprevir
 - clarithromycin
 - cobicistat
 - conivaptan
 - danoprevir and ritonavir
 - diltiazem
 - elvitegravir and ritonavir
 - regular grapefruit juice consumption
 - idelalisib
 - indinavir and ritonavir
 - itraconazole
 - ketoconazole
 - lopinavir and ritonavir
 - nefazodone
 - nelfinavir
 - paritaprevir and ritonavir and (ombitasvir and/or dasabuvir)
 - posaconazole
 - ritonavir

- saquinavir and ritonavir
- telaprevir
- tipranavir and ritonavir
- troleandomycin
- voriconazole

Within 2 weeks prior to Baseline through the Follow-up period

- High-potency topical corticosteroids (Class 1-3). The use of low- to mid-potency topical corticosteroids (Class 4-7), inhaled corticosteroids, or intranasal corticosteroids will be allowed.
- Use of crisaborole ointment.
- Systemic antibiotics.
- Bleach baths or topical coal tar.
- Topical calcineurin inhibitor use (e.g., pimecrolimus, tacrolimus).
- New onset use of systemic antihistamines.
- UVA or UVB phototherapy
- Topical and oral antibiotics/antiviral/antifungal/antiseptic agents
- Topical probiotics
- Topical antihistamines.
- The use of intranasal and oral antihistamines will be allowed^a.
- a Subjects following stable regimens (≥2 weeks consistent for intranasal and 3 months for oral use before study baseline) with systemic antihistamines are permitted to continue use but should not alter the dose or stop the regimen while in the study within 1 week prior to Baseline.

Biologics

- Cell-depleting agents, including but not limited to rituximab: within 6 months of baseline.
- Infliximab, adalimumab, golimumab, certolizumab pegol, abatacept, etanercept, anakinra, and dupilumab: within 12 weeks of baseline, or 5 half-lives, whichever is longer.
- Other biologics: within 12 weeks of Baseline, or 5 half-lives (if known), whichever is longer.

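### Appendix B prints look-back windows that contradict Section 6.3 or its own entries, for allergen immunotherapy, Class 1-3 topical steroids and phototherapy, cell-depleting agents and oral H1 antihistamines

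*Protocol*

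**What the plan says.** Section 6.3 counts its look-back periods from randomization. It sets four weeks for Class III or stronger topical steroids and topical anti-pruritics (no. 4), and four weeks for systemic immunosuppressants and phototherapy (no. 7). Allergen immunotherapy is six months (no. 11). All biologics get the longer of 12 weeks and five half-lives (no. 8). SAP 4.1.1.2 repeats these rules. Sections 6.2 no. 2a and 6.3 no. 5a allow oral H1 antihistamines at stable doses and give no duration.

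Appendix B has a list headed "Within 4 weeks prior to Baseline through the Follow-up period" and a second headed "Within 2 weeks prior to Baseline through the Follow-up period". The first contains "Class III or higher topical corticosteroids or any topical anti-pruritic therapies", phototherapy (within the systemic immunosuppressant entry) and allergen immunotherapy. The second repeats the top steroid classes, as "High-potency topical corticosteroids (Class 1-3" (bracket left open here), and "UVA or UVB phototherapy". It also bars newly started systemic antihistamines, while footnote a speaks of three months of consistent oral use. The separate Biologics block gives cell-depleting agents six months.

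On status, Appendix B states: "The use of an excluded medication/therapy is a protocol violation and must be recorded in the CRF". Section 25 makes appendices part of the protocol. Section 7.2 makes randomization conditional on meeting no exclusion criterion. Sections 8.13.2 and 10.6.2 send sites to Appendix B, and Section 8.13 refers questions about prior or concomitant therapy to the Medical Monitor. No text ranks Appendix B against Section 6 or says that the longest window applies.

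**The concern.** Sections 6.2 and 6.3 allow no eligibility deviations, so thresholds should read the same wherever a site looks. Here they do not, and two kinds of error follow.

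A site working from Appendix B can enrol a subject whom 6.3 excludes. Allergen immunotherapy last given on Day -60 looks acceptable in Appendix B and is barred by 6.3 no. 11.

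A site working from Section 6 can randomize a subject who is already in breach of Appendix B. A short half-life cell-depleting agent given on Day -100 passes 6.3 no. 8 and falls inside the six months of Appendix B.

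Either way, sites and deviation reviewers may classify the same subject differently. Section 12.7 requires unmet entry criteria and non-permitted concomitant medications to be summarized, so the deviation tables would carry that inconsistency.

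**Working it through.** The plan gives no figure to reproduce. The check sets the windows side by side and counts days. Assumptions: randomization takes place at Baseline (Day 0), six months is 182 days and three months is 91 days.

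| Class | Section 6 | Appendix B | Gap |
|---|---|---|---|
| Allergen immunotherapy | 6 months | 4 weeks only | 182 - 28 = 154 days |
| Class 1-3 topical steroids | 4 weeks | 4 weeks and 2 weeks | 28 - 14 = 14 days at most |
| Phototherapy | 4 weeks | 4 weeks and 2 weeks | 28 - 14 = 14 days at most |
| Cell-depleting agents | max(84 days, 5 half-lives) | 6 months | 182 - max(84, 5 × half-life) |
| Oral H1 antihistamines | stable, no duration | not new within 2 weeks; 3 months in footnote a | see below |

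**Steroids and phototherapy.** Section 8.13.2 bars listed therapies from the Screening visit, which falls between Day -21 and Day -14. The days on which the two-week entry passes a subject whom 6.3 excludes are therefore:
- Screening on Day -14: Day -28 to -15, which is 14 days.
- Screening on Day -21: Day -28 to -22, which is 7 days.

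Example: a Class 2 steroid used on Day -25, with Screening on Day -16, passes the two-week entry and fails both the four-week entry and 6.3 no. 4.

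**Cell-depleting agents.** The documents give no half-life, so a range is shown.
- Up to 16.8 days (84/5): 182 - 84 = 98 days.
- 20 days: 182 - 100 = 82.
- 25 days: 182 - 125 = 57.
- 30 days: 182 - 150 = 32.
- 36.4 days (182/5): zero. Above this, 6.3 no. 8 is the longer rule; at 40 days it is longer by 200 - 182 = 18 days.

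Taking six months as 181 to 184 days moves the crossover only to 36.2-36.8 days. Example: last dose on Day -100 with an assumed half-life of 10 days. Five half-lives are 50 days, so the 6.3 window is 84 days; 84 < 100 < 182. The subject passes 6.3 and breaches Appendix B.

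**Oral H1 antihistamines.** A start on Day -91 gives 91 days and meets footnote a. Starts from Day -90 to Day -15 (76 dates) fall short of it but are not new within two weeks. If the drug must also have been started before a Screening visit on Day -21, the range is Day -90 to -22 (69 dates). Example: a constant dose begun on Day -40 breaks no duration stated in Section 6 and falls short of footnote a.

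**The case against.** **Most of this is already resolved.** For immunotherapy, the top steroid classes and phototherapy, Section 7.2 makes the 6.3 window binding. For steroids and phototherapy, Appendix B also carries the right window in its four-week list. This stands. A reader might infer that Appendix B authorizes enrolment of subjects whom 6.3 excludes. It does not; it is a misleading working list.

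**The remaining rules are cumulative.** A site that applies the longest rule obeys everything, and footnote a can be read as defining what stable means in Section 6. On that reading the Day -40 starter is simply not stable. This is a fair reading, and it means that neither a contradiction nor forced study-drug discontinuation under Section 8.9 is established. But Section 6 does not point to the footnote, and the two-week entry beside it suggests a different threshold. For cell-depleting agents no text says to take the longer rule. Referral to the Medical Monitor helps only a site that notices the question.

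**Topical antihistamines.** A reader might add "Topical antihistamines" as a further clear conflict, since they sit in the two-week list while any topical anti-pruritic is barred for four weeks. The documents do not define anti-pruritic, so the conflict depends on the reader's classification.

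**Effect on the analyses.** A reader might infer damage to the trial's main result. mITT membership turns on randomization, at least one dose and a post-baseline visit, none of which depends on these windows. A pre-study dose is prior therapy, so a Day -100 cell-depleting dose fits neither Section 12.7 category neatly, though that list is a stated minimum. Per-protocol membership changes only if such a deviation is graded major under the guidance cited in SAP 7.3.2, which is not among the documents.

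**Conclusion.** Appendix B is wrong as printed for allergen immunotherapy (about 154 days too short) and for the two-week steroid and phototherapy entries (7 to 14 days, depending on the Screening date). In these classes 6.3 still decides eligibility. For cell-depleting agents, a subject can satisfy 6.3 and breach Appendix B over a span of up to 98 days when the half-life is below about 36 days. For oral H1 antihistamines, the only stated duration sits in a footnote that Section 6 does not cite, leaving 69 to 76 start dates open to differing classification.

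This is a drafting inconsistency that should be corrected. It bears on site eligibility decisions and deviation reporting, not on the mITT population, power or type I error. The day counts rest on the month lengths above and on assumed half-lives. The documents give no basis for estimating how many subjects are affected.

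**What to change.** 1. **Allergen immunotherapy:** set it to six months in Appendix B, keeping the on-study bar through follow-up.
2. **Class 1-3 topical steroids and phototherapy:** delete the two-week entries. Keep the sentence that shares the steroid bullet: "The use of low- to mid-potency topical corticosteroids (Class 4-7), inhaled corticosteroids, or intranasal corticosteroids will be allowed".
3. **Cell-depleting agents:** write one rule, the longer of six months and five half-lives, into 6.3 no. 8, the synopsis, SAP 4.1.1.2 and the Biologics block of Appendix B.
4. **Oral H1 antihistamines:** state footnote a's three-month stability period in 6.2 no. 2a, 6.3 no. 5a, the synopsis and SAP 4.1.1.1 and 4.1.1.2. Align the new-onset entry for oral use and leave the two-week rule for intranasal use. Repair the end of footnote a, where an on-study instruction runs into a stray one-week pre-Baseline limit.
5. **Topical antihistamines (optional):** move them to four weeks only if the sponsor regards them as topical anti-pruritics.

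A single sentence saying that the longest window applies would be a cheaper stopgap, but Appendix B would still print only four weeks for immunotherapy.

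The cost is text edits, IRB approval with the next amendment, and a few more early screen failures. These would be mainly recent starters of oral H1 antihistamines and cell-depleting agent users between the two current windows.
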